6.4.4. Actigraphy assessment

Actigraphy is a non-invasive method of monitoring a person's rest and activity cycles. The movements the actigraphy sensor undergoes are continually recorded.

The sponsor will provide the investigator with actigraphy sensors for the trial subjects and a notebook computer to read out data. The actigraphy data will be transferred to (), where they will be further processed and stored.

Actigraphy assessments will be performed for 3 days prior to baseline and for 3 days at the end of each treatment period. At phone call visits VS2, V1A, V2A and V3A, trial staff will call the subjects and remind them to put on their actigraphy sensor bracelet and wear it until the next on-site visit.

6.4.5. Subject diaries

The paper-based subject diaries are intended for the daily documentation of

- Get-up time
- Total time (hours) slept last night
- Wake-up periods during night sleep
- Time of drug intake (except screening phase diary)
- Number of capsules taken (except screening phase diary)
- Somnolence episodes
- Diurnal involuntary sleep attacks
- Voluntary naps
- Number of caffeinated drinks
- Going-to-bed time

The diaries will be translated in the local languages of the countries involved. Only the subject is allowed to make any entry in the diaries. In case of difficulties with writing, however, a caregiver may help.

The subject will complete four paper diaries: One screening phase diary (started at VS1, without time of IMP intake and number of capsules taken) and treatment phase diaries (started at VR, V1C and V2C) for each treatment period. The subject has to bring the diaries for inspection by the investigator at all visits. The screening phase diary will be collected at VR, the treatment phase diaries will be collected at V1C, V2C and V3B.

Thus, the diaries will be completed continuously from VS1 to V3B, i.e. also during the washout periods after treatment periods I and II.

6.5. Pharmacokinetics (PK)

For PK laboratory tests, approximately 4.5 mL of blood will be collected at each blood withdrawal. The sample will be taken when the subject arrives on the site. The times of blood withdrawal must be recorded. Modafinil and flecainide concentrations in plasma will be measured by a central laboratory (for contact details, see Section 14.1) using a validated LC-MS/MS method.

7. ADVERSE EVENT, PREGNANCY AND EMERGENCY

7.1. Adverse Event (AE)

7.1.1. Definition of an adverse event

An adverse event is any untoward medical occurrence in a clinical trial subject administered a medicinal product and which does not necessarily have a causal relationship with this treatment.

AEs can be symptoms, signs, or clinically relevant laboratory abnormalities occurring during the course of the trial.

All other medical conditions, which are present at VS1, should not be considered as AEs unless a worsening in severity or frequency has occurred during the trial. These medical conditions should be adequately documented on the appropriate page of the eCRF.

When reporting abnormal laboratory results on the AE pages of the eCRF, a clinical diagnosis should be recorded rather than the abnormal value itself if this is available (e.g. “anaemia” rather than “decreased red blood cell count” or “haemoglobin = 10.5 g/dL”).

In case of surgical or diagnostic procedures, the condition/illness leading to such a procedure is considered as the AE rather than the procedure itself.

7.1.2. Severity assessment

The investigator must systematically assess the severity of adverse events according to the following definitions:

- **Mild:** a type of adverse event that is usually transient and may require only minimal treatment or therapeutic intervention. The event does not generally interfere with usual activities of daily living.
- **Moderate:** a type of adverse event that is usually alleviated with additional specific therapeutic intervention. The event interferes with usual activities of daily living, causing discomfort but poses no significant or permanent risk of harm to the research participant.
- **Severe:** a type of adverse event that requires intensive therapeutic intervention. The event interrupts usual activities of daily living, or significantly affects clinical status. The event possesses a significant risk of harm to the research participant and hospitalisation may be required.

Changes in the severity of an AE should be documented as a new AE. Adverse events characterised as intermittent requires documentation of the onset and duration of each episode.

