3. TRIAL DESIGN

3.1. Overall Trial Design and Plan

This is a prospective, double-blind, randomised, controlled trial using a complete 3-way cross-over design. Subjects will attend the site for twelve visits. The seven trial periods are depicted in Table 2.

Table 2: Trial design

Screening	Treatment I	Washout I*	Treatment II	Washout II*	Treatment III	Follow-Up
1-2 weeks	2 weeks	1(2) weeks	2 weeks	1(2) weeks	2 weeks	1 week
No treatment	A, B, or C	No treatment	A, B, or C	No treatment	A, B, or C	No treatment

(Dose A = placebo; Dose B = THN102 200 mg/2 mg; Dose C = THN102 200 mg/18 mg.)

*Washout periods can be extended to up to 2 weeks, if this is more convenient for the subject.

The trial procedures by visit are presented in the flow chart on Page 12.

At visit VR the subjects will be equally randomised (1:1:1:1:1) double-blind to a treatment sequence containing three periods (shown in Table 3).

Table 3: Treatment sequences

Sequence	Treatment period I	Treatment period II	Treatment period III
1	Dose A	Dose B	Dose C
2	Dose B	Dose C	Dose A
3	Dose C	Dose A	Dose B
4	Dose A	Dose C	Dose B
5	Dose C	Dose B	Dose A
6	Dose B	Dose A	Dose C

The duration of each treatment period is 2 weeks, with a 1-week washout in between (to avoid carry-over effects) and 1-week follow-up period after the last treatment period. Washout periods can be extended up to two weeks. THN102 will be administered orally once daily.

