8.3.2. Safety

Safety parameters will be analysed as follows:

Vital signs: All vital signs data will be listed by treatment, subject, and visit/time and will be flagged vs. predefined clinical normal range. The mean value of vital sign parameter assessments during a visit will be summarized. Summary statistics will be provided by treatment and visit/time. Shift tables will be provided for vital sign abnormality change from baseline to endpoint within each treatment period.

ECG parameters: All ECG parameters data will be listed by treatment, subject, and visit/time and abnormalities will be flagged vs. predefined clinical normal range. Summary statistics will be provided by treatment and visit/time.

A shift table will be prepared to document QT change and distribution vs. baseline.

C-SSRS: C-SSRS score data will be listed by treatment, subject, and visit/time. Summary statistics will be provided by treatment and visit/time.

QUIP-RS: QUIP-RS score data will be listed by treatment, subject and visit/time. Summary statistics will be provided by treatment and visit/time.

MDS-UPDRS: MDS-UPDRS score data will be listed by treatment, subject and visit/time. Summary statistics for each part of the MDS-UPDRS as well as the total score will be provided by treatment and visit/time.

Clinical laboratory evaluations: All laboratory data will be listed by treatment, subject, and visit/time and abnormalities will be flagged vs. common normal range if considered by investigator as clinically relevant. Summary statistics will be provided by treatment and visit/time. Shift tables will be provided for clinical laboratory variables' change from baseline to endpoint.

Adverse events: All information obtained on adverse events will be displayed by treatment and subject after coding with pertinent MedDRA version. All adverse events and related adverse events will be presented. The number and percentage of subjects with adverse events will be tabulated by body system and preferred term with a breakdown by treatment. An adverse event starting in one period and continuing into the next period is counted only in the onset period. A subject with multiple adverse events within a body system is only counted once towards the total of this body system.

Concomitant medications / Significant non-drug therapies: All concomitant therapies will be coded by WHO version and listed by treatment group and subject.

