##### Treatment periods

The periods from the day after visits VR, V1C, and V2C, to the dates of visits V1B, V2B, and V3B respectively, will be defined as the three treatment periods of this trial.

Data collected at visits V1B, V2B, and V3B will be considered as end-of-treatment values for their respective treatment periods.

If an early discontinuation visit (EDV) occurs after 7 or more IMP intakes, and not more than 3 days after the last IMP intake, the data collected at the EDV will be assigned to the end of the ongoing treatment period for statistical analyses.

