### 5.5.1 Adverse Events

AEs will be coded according to MedDRA Version 21.0.

Adverse event data includes:

- adverse event name
- start date
- stop date or ongoing
- severity (mild, moderate, severe)
- relationship to the IMP (unrelated, unlikely, possible, probable, definite)
- action taken with IMP (no action, drug interrupted, drug withdrawn, unknown)
- other actions (none, medication required, tests required, hospitalisation required or prolonged, other)

- outcome (recovered/resolved, recovered/resolved with sequelae, recovering/resolving, not recovered/not resolved, fatal, unknown) and date of outcome
- serious (yes or no)

All AEs will be presented in listings.

Adverse event summaries will focus on **treatment-emergent adverse events (TEAEs)**, defined as AEs with an onset or worsening after the first IMP intake and not more than 7 days after the last IMP intake.

If the start date of an AE is incomplete or missing, it will be assumed to be treatment-emergent except if the stop date or the incomplete start date indicates that the event started prior to the first IMP intake or later than 7 days after the last IMP intake.

Treatment-emergent adverse events will be assigned to treatments based on the treatment period containing the AE onset date. If the onset date of an adverse event is during a washout period, it will be assigned to the preceding treatment period. If the AE onset date is incomplete such that it could belong to more than one treatment period, the AE will be assigned to all treatments corresponding to such treatment periods.

Based on collected data the following will be determined and will be used in addition to AEs overall for presentation in the applicable tables and listings:

- **Serious Adverse Events (SAEs):** defined as AEs considered by the investigator as serious.
- **Related TEAEs:** defined as AEs with relationships to the IMP assessed as being “possible”, “probable” or “definite” and include AEs with missing IMP relationship assessments.
- **Unrelated TEAEs:** defined as AEs with relationships to the IMP assessed as being “unlikely” or “unrelated”.
- **Severe TEAEs:** defined as AEs assessed as being “severe” in intensity and include the events with missing severity assessment.
- **TEAEs leading to discontinuation:** defined AEs whose action taken with IMP is “drug withdrawn” or other action taken is “withdrawal from trial”.

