- **TEAEs leading to death:** selected as those events where outcome of event is indicated as “fatal”.

The **duration of the AE** will be calculated using the following formula:

$$AE \text{ Duration (days)} = AE \text{ stop date} - AE \text{ start date} + 1$$

If the start or stop dates of the AE are incomplete or AE is still ongoing at the end of the trial, the duration will not be calculated.

The following tables and listings will be provided:

Table 15.2.1.1.1.S Overall Summary of TEAEs – Safety

Table 15.2.1.1.2.T Overall Summary of TEAEs – Safety

An overview of TEAEs:

- TEAE
- Non-Serious TEAE
- Serious TEAE
- Related TEAE
- Related Serious TEAE
- Severe TEAE
- TEAE leading to discontinuation
- Serious TEAE leading to discontinuation
- Related TEAE leading to discontinuation
- TEAE leading to death

will be displayed for the subjects in the safety set.

Table 15.2.1.2.T Incidence of TEAEs – Safety

Table 15.2.1.3.T Incidence of Non-Serious TEAEs – Safety

Table 15.2.1.4.T Incidence of Serious TEAEs – Safety

Table 15.2.1.5.T Incidence of Related TEAEs – Safety

Table 15.2.1.6.T Incidence of Related Serious TEAEs – Safety

Table 15.2.1.7.T Incidence of TEAEs Leading to Discontinuation – Safety

Table 15.2.1.8.T Incidence of TEAEs Leading to Death – Safety

TEAEs will be summarised by displaying the numbers of adverse events, as well as counts and percentages of subjects having experienced adverse events. Percentages will be based on the number of subjects in the safety set. SOC and PTs within each SOC will be ordered by descending overall incidence.

Table 15.2.1.9.T Incidence of TEAEs by Severity – Safety

TEAEs will be summarised similarly as above within each adverse event severity level.

All adverse event data will be listed as follows:

Listing 16.2.6.1 Adverse Events: MedDRA Coding

Listing 16.2.6.2 Adverse Events: General – Enrolled

Listing 16.2.6.3 Serious Adverse Events – Safety

Listing 16.2.6.4 AEs Leading to Discontinuation – Safety

Listing 16.2.6.5 AEs Leading to Death – Safety

All AEs will be displayed by subject including the PT of an AE, start and stop dates, duration and other characteristics of AEs.

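### A new AE record for every severity change, including improvement, with no rule linking records, double-counts easing events and can place a few on the wrong treatment

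*Protocol*

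**What the plan says.** Recording (Protocol 7.1.2): "Changes in the severity of an AE should be documented as a new AE". The same section asks for the onset and duration of each episode of an intermittent AE.

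Counting across periods (Protocol 8.3.2): "An adverse event starting in one period and continuing into the next period is counted only in the onset period".

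Treatment emergence (SAP 5.5.1): TEAEs are "defined as AEs with an onset or worsening after the first IMP intake and not more than 7 days after the last IMP intake". Protocol 7.1.4 uses the same onset-or-worsening test.

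Attribution (SAP 5.5.1): "Treatment-emergent adverse events will be assigned to treatments based on the treatment period containing the AE onset date". For the gaps between treatment periods: "If the onset date of an adverse event is during a washout period, it will be assigned to the preceding treatment period".

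Display (SAP 5.5.1): "TEAEs will be summarised by displaying the numbers of adverse events, as well as counts and percentages of subjects having experienced adverse events". Percentages use the Safety Set. A further table repeats the summary within each severity level.

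SAP 5.5.1 does not repeat the Protocol 8.3.2 rule. SAP Section 7 lists one departure from the protocol, the Per Protocol set, so the rule is not withdrawn either. Neither document says which start date a severity-change record carries, how it is tied to its parent, or whether a record opened by improvement is left out of the TEAE tables.

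**The concern.** The documents elsewhere treat only worsening as new: in the AE definition for conditions present at VS1 (Protocol 7.1.1) and in both TEAE definitions. The recording rule is wider. When an event eases, a second record is opened. If its start date is the date of easing, that record has an onset after first intake and passes the TEAE test although the subject got better.

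Two things are at stake. Event numbers are tabulated, so one clinical event can appear as two, and in the severity table under two severities. In a crossover, an onset in a later treatment period also moves the second record into another treatment's column. Safety versus placebo is the primary objective. If AEs are more frequent on the active doses, such records would tend to add to placebo and narrow the contrast.

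**Working it through.** The plan gives no figure on this point to reproduce. The check traces the rules and then sizes the effect.

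**Inputs.** The rules above. SAP 4.6 defines the treatment periods as "The periods from the day after visits VR, V1C, and V2C, to the dates of visits V1B, V2B, and V3B respectively", so a washout separates each pair. Protocol 3.1 gives a washout of 1 week, extendable to 2, and the six sequences. Protocol 8.5 gives 60 randomised subjects.

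**Trace.** An event starts on treatment X and later eases. The new record is assumed to start on the date of easing.

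| The event eases | New record assigned to | Events | Subjects with the term |
|---|---|---|---|
| in the same treatment period | X, correct | +1 on X | unchanged |
| in the washout after X | X, correct (washout rule) | +1 on X | unchanged |
| in the next treatment period, on Y | Y, wrong | +1 on Y | +1 on Y, unless the subject already has the term there |

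A fourth case is an AE that began between consent and first intake and eases during or just after treatment period I. Its new record is a TEAE of the first treatment although nothing worsened.

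**Size per event.** In the third case one subject is added to a wrong column: 1/60 = 1.7 percentage points, if all 60 are dosed.

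**Direction.** The six sequences contain 6 × 2 = 12 treatment-to-treatment transitions, each ordered pair occurring twice. Eight start from an active dose and four of those lead to placebo, so placebo directly follows an active dose in four of the six sequences.

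**Illustration with assumed rates (none is in the documents).** Let true incidence be 10% on placebo and 30% on each active dose. Let f be the share of events that outlast the washout and then ease in the next treatment period, with independence between periods. Observed incidence on a treatment is the mean over the six sequences of 1 − (1 − p)(1 − f × p_prev), where p_prev is the incidence on the preceding treatment (0 in period I).

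- Placebo: 0.10 + (4/6) × 0.90 × 0.30f = 0.10 + 0.18f
- Active dose: 0.30 + 0.70 × f × (2 × 0.10 + 2 × 0.30)/6 = 0.30 + 0.0933f
- Difference: 0.20 − 0.0867f

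| f | Placebo | Active | Difference (points) |
|---|---|---|---|
| 0 | 10.0% | 30.0% | 20.0 |
| 2% | 10.4% | 30.2% | 19.8 |
| 5% | 10.9% | 30.5% | 19.6 |
| 10% | 11.8% | 30.9% | 19.1 |
| 20% | 13.6% | 31.9% | 18.3 |

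With assumed incidences of 20% and 40%, the difference at f = 20% is 18.1 points.

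**The case against.** The strongest reply is that the usual case is attributed correctly. What follows a treatment period is a washout, and SAP 5.5.1 gives washout onsets to the preceding treatment. Protocol Table 1 lists terminal half-lives of 15 h for modafinil and 13 h for flecainide. Seven days is 168 h, or 168/15 = 11.2 and 168/13 = 12.9 half-lives, so a drug effect lasting into the next treatment period should be uncommon. This stands. A reader might infer that any event easing after its own period lands on the wrong treatment; the washout rule excludes that.

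Second, an improvement is neither a worsening nor a fresh clinical onset, the documents do not state the split record's start date, and Protocol 11.1 leaves further detail to a data management plan not seen here. So the miscount is the literal reading, not a certainty. But the SAP says nothing that would stop a programmer from following it.

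Third, Protocol 8.3.2 already shows the intent, and its once-per-body-system rule limits repeats. The intent is clear, but a record with its own onset escapes the first rule, and counting once within a treatment column does not remove the subject from a second column.

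Fourth, the AE analysis is descriptive, with no test or threshold, and the listings show start and stop dates, so a careful reader could find split chains. That limits the harm but does not correct the tables.

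Fifth, the pre-treatment case is narrow, because conditions present at VS1 are not AEs unless they worsen. This also stands.

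**Conclusion.** Followed literally, the written rules give a wrong count: extra events whenever an AE eases, attribution to the wrong treatment when it outlasts the washout and eases in the next treatment period, and a false TEAE when a pre-treatment AE eases after first intake. Protocol 7.1.2, Protocol 8.3.2 and SAP 5.5.1 have not been reconciled for split records.

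The effect on subject incidence is probably small: at most 1.7 points in one column per affected event. Under the assumed rates, a 20.0-point difference falls to between 19.8 and 18.3 as f goes from 2% to 20%. This rests on the new record starting at the date of easing and on shares that the documents do not supply.

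A reader might also infer a large inflation of event counts. The documents do not support a figure: they do not say how many AEs change severity, and some changes would be worsenings, which properly count as new TEAEs. Easing within the same period or in the washout leaves subject incidence unchanged. The point merits correction because the tables serve the primary objective and no new data are needed.

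**What to change.** Amend SAP 5.5.1 as follows.

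- State the Protocol 8.3.2 rule and say that it applies to events split by a severity change.
- At blind review, link contiguous records of the same event: same subject, same preferred term, start on or one day after the previous stop. Exclude episodes recorded as intermittent.
- Count a linked record as a new TEAE only if its severity is higher than that of the record before it, in line with the worsening limb of the TEAE definition.
- Otherwise keep one event at maximum severity under the treatment of the first record. If the first record predates first intake, do not count the easing record as a TEAE.

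The cost is SAP wording and a small record-linking step on data already collected. The SAP reports that the blind review meeting took place on 10 February 2020, so the step would be an addition to that review, completed before unblinding. The risk is that separate back-to-back episodes with the same term are merged; the linked chains should be checked for this while treatment is still masked.

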7.1.3. Relationship assessment

The investigator must systematically assess the relationship of adverse events to the IMP using the following definitions:

- **Unrelated:** A clinical event with no evidence of any causal relationship.
- **Unlikely:** A clinical event, including laboratory test abnormality, with a temporal relationship to drug administration which makes a causal relationship improbable, and in which other drugs, chemicals or underlying disease provide plausible explanations.
- **Possible:** A clinical event, including laboratory test abnormality, with a reasonable time sequence to administration of the drug, but which could also be explained by concurrent disease or other drugs or chemicals. Information on drug withdrawal may be lacking or unclear.
- **Probable:** A clinical event, including laboratory test abnormality, with a reasonable time sequence to administration of the drug, unlikely to be attributed to concurrent disease or other drugs or chemicals, and which follows a clinically reasonable response on withdrawal (dechallenge). Rechallenge information is not required to fulfil this definition.

- **Definite:** A clinical event, including laboratory test abnormality, occurring in a plausible time relationship to drug administration, and which cannot be explained by concurrent disease or other drugs or chemicals. The response to withdrawal of the drug (dechallenge) should be clinically plausible. The event must be definitive pharmacologically or phenomenologically, using a satisfactory rechallenge procedure if necessary.

The relationship to IMP can be modified during the trial or AE assessment. For example, although an AE may rate only as “possibly” related to IMP soon after discovery, it can be flagged as requiring more information and later be upgraded to “probably”. Changes in the assessment of relationship to IMP should be clearly documented.

Mapping to the two categories “related” and “unrelated”: The categories “unrelated” and “unlikely” will be mapped to “unrelated”, the categories “possible”, “probable” and “definite” will be mapped to “related”.

